11 CHANGES OR CLARIFICATIONS TO ANALYSES PLANNED IN THE STUDY PROTOCOL

11.1 Changes to the analyses planned in the study protocol

11.1.1 Change in pharmacodynamic variable

The protocol section 10.2.4.2 describes the following PD variable: *% of subjects at 8 h after study treatment injection with PRU value < 100 or > 1.05 × baseline value*.

The intent of this variable was to estimate the proportion of subjects still with a low value of platelet aggregation 8 hours after administration of study drug. This is assuming that a baseline platelet aggregation (PRU_{baseline}) value ≥ 100 .

As some subjects may have a PRU_{baseline} value < 100 , and a PRU_{8h} < 100 , it is not sensible to consider those subjects in the group of subjects with still significantly low platelet aggregation after study drug administration. Unless the PRU_{8h} is lower than PRU_{baseline}.

For this purpose, and to be consistent with the intent of assessing back to normal/baseline value, the definition of this variable should be modified to: *% of subjects at 8 h after study treatment injection with PRU value < 100 or < 0.95 × baseline value*.

11.2 Changes in the conduct of the study / data collection

Not applicable.

11.3 Clarifications concerning endpoint definitions and related variables or statistical methods

Not applicable.

11.4 Additional analyses as compared to the study protocol

Not applicable.

12 LIST OF TABLES, LISTINGS AND FIGURES

For the complete list of tables, listings and figures, please refer to the *SAP Appendix - List of statistical outputs* document.

13 APPENDICES

Appendix A Protocol synopsis

PROTOCOL SYNOPSIS ID-076A201

TITLE	A multi-center, double-blind, randomized, placebo-controlled study to assess the pharmacodynamics, pharmacokinetics, tolerability, and safety of a single subcutaneous injection of ACT-246475 in adults with stable coronary artery disease.
OBJECTIVES	Primary objective(s) The primary objective of the study is to characterize inhibition of platelet aggregation (IPA) relatively to placebo after a single subcutaneous (s.c.) injection of ACT-246475 either in the thigh or in the abdomen at 2 different doses in subjects with stable coronary artery disease (CAD) receiving conventional background oral antiplatelet therapy (e.g., acetylsalicylic acid, P2Y ₁₂ receptor antagonists). Other objectives The other objectives of this study are described in Section 2.2.
DESIGN	This is a prospective, multi-national, multi-center, double-blind, randomized, placebo-controlled, parallel-group, Phase 2, exploratory study of a single s.c. administration of ACT-246475, at 2 different dose levels, in subjects with stable CAD receiving conventional background therapy (e.g., acetylsalicylic acid, P2Y ₁₂ receptor antagonists, etc.). Approximately 324 adult subjects with stable CAD will be randomized into 1 of the 8 combinations of the treatment, dose, and injection site using a 2:2:2:2:1:1:1:1 ratio:

	<pre> graph TD Randomization[Randomization] --> ACT[ACT-246475] Randomization --> Placebo[Placebo] ACT --> 8mg[8 mg] ACT --> 16mg[16 mg] Placebo --> 8mg[8 mg] Placebo --> 16mg[16 mg] 8mg --> Thigh1[Injection: Thigh] 8mg --> Abdomen1[Injection: Abdomen] 16mg --> Thigh2[Injection: Thigh] 16mg --> Abdomen2[Injection: Abdomen] 8mg --> Thigh3[Injection: Thigh] 8mg --> Abdomen3[Injection: Abdomen] 16mg --> Thigh4[Injection: Thigh] 16mg --> Abdomen4[Injection: Abdomen] Thigh1[54 subjects] Abdomen1[54 subjects] Thigh2[54 subjects] Abdomen2[54 subjects] Thigh3[27 subjects] Abdomen3[27 subjects] Thigh4[27 subjects] Abdomen4[27 subjects] </pre>
	
Each subject will receive a single s.c. administration of either 8 mg ACT-246475, 16 mg ACT-246475 or matching placebo, either in the thigh or in the abdomen.
 
Double-blinding will apply to treatment (ACT-246475 vs placebo). The dose (8 mg vs 16 mg) will be single blinded (subject blinded). The injection site (thigh vs abdomen) will not be blinded.
 
Treatment group allocation will be stratified based on baseline platelet reactivity value (expressed as P2Y₁₂ reaction units [PRU]) measured on Day 1 by the VerifyNow® assay before ACT-246475 injection considering the 3 following categories: high reactivity (PRU > 250), medium reactivity (150 ≤ PRU ≤ 250), and low reactivity (PRU < 150).
 
The study comprises the following consecutive periods:
 
Screening period: Lasts 1 to 21 days; starts with the signature of the informed consent form and ends on Day -1.
 
Treatment period: Lasts 2 days: Day 1 and Day 2.
 
Follow-up period: Lasts 28 to 35 days. Starts on Day 3 and ends with the safety follow-up telephone call.

PLANNED DURATION	Approximately 7 months from first subject, first visit to last subject, last visit.

SITE(S) / COUNTRY(IES)	Approximately 20 sites in 5–10 countries are planned.
INCLUSION CRITERIA	
1. Signed informed consent prior to any study-mandated procedure.2. Male and female subjects aged from 18–85 years, inclusive.3. For women of childbearing potential: Negative urine pregnancy test at Visit 1 and at Visit 2 before randomization.4. Stable CAD defined by the presence of any of the following conditions:
a. History of CAD with coronary artery stenosis on coronary angiogram $\geq 50\%$.b. Previously documented myocardial infarction occurring more than 3 months prior to randomization.5. Antiplatelet background therapy stable for at least 1 month prior to randomization.6. Body weight ≥ 40.0 kg (88.2 lbs).
EXCLUSION CRITERIA	
Conditions associated with atherosclerosis:
 
1. Acute coronary syndrome, percutaneous coronary intervention or any intervention for peripheral artery disease within 3 months prior to randomization.2. Acute ischemic stroke or transient ischemic attack within 3 months prior to randomization. 
Mitigation of bleeding risks:
 
3. Active internal bleeding, or medical history of recent (< 1 month) bleeding disorders or conditions associated with high risk of bleeding (e.g., clotting disturbances, gastrointestinal bleed, hemoptysis).4. Hemoglobin ≤ 10 g/dL at screening.5. Loss of at least 250 mL of blood within 3 months of screening.6. Use of anticoagulants (oral, parenteral) or fibrinolytic therapy within 24 h prior to screening (Visit 1).7. Known platelet disorders (e.g., thrombasthenia, thrombocytopenia, von Willebrand disease).

	
Conditions that may prevent subject from complying with study requirements or may be a confounder for the study interpretation:
 
8. Pregnant or breastfeeding women.9. Uncontrolled hypertension according to investigator's judgment.10. Known and documented moderate or severe hepatic impairment.11. End-stage renal failure requiring dialysis.12. Any clinically significant findings on a physical exam, or laboratory tests prior to screening that in the investigator's judgment would preclude safe or reliable participation of a subject in the study.13. Concomitant diseases (e.g., advanced liver cirrhosis, mental illness, neurodegenerative disease, terminal malignancy, etc.) or conditions (e.g., inability to communicate well with the investigator in the local language) that, in the opinion of the investigator, may prevent subject from complying with study requirements or may be a confounder for the study interpretation.14. Veins unsuitable for intravenous puncture on either arm (e.g., difficult to locate, access, or puncture) according to the investigator's judgment.15. Clinically relevant skin disease that prevents s.c. injection in the thigh or abdomen, according to the investigator's judgment.16. Use of inhibitors of organic anion-transporting polypeptide (OATP)1B1 or OATP1B3 at screening (Visit 1).17. Known hypersensitivity to ACT-246475, any of its excipients, or drugs of the P2Y12 class.18. Previous exposure to investigational drug within 3 months prior to screening.
STUDY TREATMENTS	
Investigational treatment and matching placebo
 
Study treatment for s.c. administration will be available as sealed glass vials in 1 strength: 20 mg. The vials contain 22 mg of lyophilized ACT-246475A (hydrochloride salt of ACT-246475) or matching placebo to be reconstituted with 1 mL of water for injection. Further dilution with 1 mL NaCl 0.9% will be

	
performed for preparation of the dose of 8 mg. The s.c. formulation contains mannitol as an inactive ingredient.
 
Study treatment will be given as a single dose of ACT-246475 (8 or 16 mg) or of matching placebo in a volume of 0.8 mL, administered s.c. at site by qualified personnel (e.g., nurse, physician).
 
The investigational treatment and its matching placebo are indistinguishable, and all treatment kits will be packaged in the same way.

CONCOMITANT THERAPY	
Allowed concomitant therapy
 
Unless medically necessary, subjects will continue their standard treatment(s) (including oral P2Y₁₂ receptor antagonists and acetylsalicylic acid) as prescribed (treatments and doses), from Visit 1 (screening) and up to the last PK or PD blood sample collection (whichever is latest).
 
Forbidden concomitant therapy
 
The following medications are prohibited from screening and up to last pharmacokinetic (PK) or pharmacodynamic (PD) blood collection (whichever is latest):
 
• Fibrinolytic therapy (e.g., streptokinase, alteplase, etc.)• Anticoagulants (e.g., Coumadin, warfarin, anti Xa inhibitors, dabigatran, heparin)• OATP1B1 and OATP1B3 inhibitors (e.g., cyclosporine, eltrombopag, lapatinib, lopinavir, rifampin, ritonavir) 
Initiation of any of the following medications is prohibited from screening up to last PK or PD blood collection (whichever is latest):
 
• Oral P2Y₁₂ receptor antagonists (e.g., clopidogrel, prasugrel, ticagrelor)• Cangrelor

ENDPOINTS	
Primary efficacy endpoint(s) Not applicable
 
Pharmacodynamic endpoints The primary PD endpoint is the PD response that is defined for each subject as a PRU < 100 starting 30 minutes after injection and lasting for at least 3 hours, as measured via the VerifyNow® assay. This corresponds to inhibition of adenosine diphosphate-induced platelet aggregation (IPA) > 80%.
 
Safety endpoints The safety endpoints will be assessed up to End-of-Study:
 
• Treatment-emergent adverse events (AEs) and serious AEs (SAEs).• All AEs and SAEs.• Change in vital signs (systolic and diastolic arterial blood pressure and pulse rate) from baseline to all assessed time points during the study.• Treatment-emergent ECG abnormalities.• Change from baseline to each measured time point in ECG variables: heart rate and the intervals: PQ/PR, QRS, QT, RR, QT corrected with Bazett's formula, QT corrected with Fridericia's formula.• Change from baseline to each measured time point for clinical laboratory tests.• Treatment-emergent marked laboratory abnormalities. 
Pharmacokinetic endpoints PK endpoints are described in Section 6.2.2.

ASSESSMENTS	Refer to the schedule of assessments in Table 2 and Table 3.
STATISTICAL METHODOLOGY	
Analysis sets The Screened analysis set includes all subjects who are screened and have a subject identification number.
 
The Randomized analysis set includes all subjects who have been assigned to a double blind study treatment.

	
The Full analysis set (FAS) includes all randomized subjects who have been administered the study treatment.
 
The Per-protocol set includes all FAS subjects who complied with protocol sufficiently to allow adequate estimation of the treatment effects (criteria for sufficient compliance will be detailed in the statistical analysis plan).
 
The Safety set includes all subjects who received at least 1 dose of study treatment.
 
The PK analysis set includes all Safety set subjects who have at least 1 PK sample collected after administration of study treatment.
 
Primary analysis
 
The analysis of the primary endpoint will be performed on the FAS comparing each active treatment dose to placebo using a 2-sided z-test at type I error level of 0.025 (corresponding to an overall level of 0.05 adjusted for multiplicity through Bonferroni method). For each active treatment arm for which comparison to placebo is statistically significant, the hypothesis that a proportion of patients achieving a response is greater than 70% will be tested at a 0.025 type I error level.
 
The study will be declared positive with regard to the primary objective arm if, for at least 1 of the 2 active treatment arms, the 2 above-described tests are sequentially rejected.
 
Additionally, longitudinal analysis of the treatment effect, from start of treatment up to 8 h after injection, on platelet reactivity as measured by VerifyNow®, i.e., PRU value, will be performed using a mixed model with PRU as dependent variable, subject as random factor, and treatment (8 mg, 16 mg, and placebo), injection site (abdomen, thigh), PRU level at randomization (stratification levels), age (continuous), gender (male, female), and assessment time (continuous) as fixed factors. The model will also include (treatment × injection site) as an interaction term to assess consistency of treatment effect across injection sites.
 
A logistic regression analysis of the PD response will be performed using the same factors as covariates.

--	--

Summary of PD response, in terms of number (%) of subjects, will be provided. IPA as measured by VerifyNow® will also be summarized as a continuous variable.

Supportive/sensitivity analyses

Consistency across the following subgroups will be assessed by repeating the primary endpoint analysis, assuming relevant number of subjects:

- Age: < 55 vs ≥ 55 years
- Body mass index: < 25.0 vs (≥ 25.0 and < 30.0) vs ≥ 30.0 kg/m^2
- Sex: male vs female
- Diabetes mellitus at baseline: yes vs no
- Chronic kidney disease: yes vs no

Additional analyses of the supportive PD endpoint (light transmission aggregometry-based PD response) will be conducted using the same approach as described for the primary PD analysis.

Sample size

The primary objective is to assess the effectiveness of ACT-246475 to allow subjects to achieve a predefined PD response; therefore, the sample size provided is sufficient to sequentially demonstrate that at least 1 of the 2 ACT-246475 doses has a higher response rate than placebo and that this response rate is greater than 70%.

The sample size required for demonstrating a difference to placebo, based on an overall type I error of 0.05 (2-sided), adjusted for multiplicity using a Bonferroni method to 0.025 for each comparison, a power of 90%, a response rate of 50% under H_0 (placebo) and 75% under H_1 is 96 per arm.

The sample size required to demonstrate that the response rate is different from 70% is based on a 2-sided type I error of 0.025, a power of 90%; and the assumptions of a response rate of 70% under H_0 and 85% under H_1 is 98 per arm.

The study should include at least 98 subjects in each treatment arm, and assuming a rate of drop-out or non-evaluable data of

	about 10%, 108 subjects should be included in each arm, giving a total of 324 subjects enrolled in the study.
STUDY COMMITTEES	A Safety Event Committee will consist of 2 independent clinical experts who will review unblinded safety data independently from the sponsor during the study. The Safety Event Committee has overall responsibility for safeguarding the interests of subjects by monitoring safety data obtained in the study and making appropriate recommendations based on the reported data. The Safety Event Committee will be fully operational prior to enrollment of the first subject into the study. The Safety Event Committee will specifically focus on study-drug-related clinically relevant major bleeding events, according to the Thrombolysis in Myocardial Infarction definition, that occur within the first 3 days after dosing.

Appendix B Protocol deviation list

The actual list of protocol deviation leading to exclusion from analysis set will be updated prior to study closure if required.

Table below provides the reason considered for excluding subjects from analysis set.

Table 7 Definition of exclusions from analysis sets

Analysis set	Reason for exclusion from analysis set	Programming conditions
Screened analysis set	Informed consent not initially obtained for the study	DV.DVREFID = IPD1D1
Randomized analysis set	Subject does not have a randomization number	Not in DS.RANDNO
Full analysis set	Subject did not get study treatment	EX.EXDOSE not >0
Safety set	Subject did not get study treatment	EX.EXDOSE not >0
Per-protocol set	Previous exposure to investigational drug	DV.DVREFID = IPD2A6
	Subject with platelet disorders at Screening	DV.DVREFID = IPD2A9
	Initiation or change in dose of oral P2Y12 during study	DV.DVREFID = IPD2D1
	Incorrect administration of study drug	DV.DVREFID = IPD2E1 or IPD3C1
	Deviation from study drug preparation instructions	DV.DVREFID = IPD2E2
	Incorrect blood sampling for platelet assays	DV.DVREFID = IPD2F2
	Background oral antiplatelet therapy not stable for 1 month prior to randomization	DV.DVREFID = IPD2A1
	Subject does not have stable coronary artery disease	DV.DVREFID = IPD2A3
	At least one post-dose VerifyNow® blood sample not evaluable (excluding the 24 h post dose)	at least one missing LB.LBSTRESN where LB.LBTESTCD= "P2Y12RU" and LB.LBTPT in (15 MIN POST-DOSE, 30 MIN POST-DOSE, 1 HOUR POST-DOSE, 2 HOURS POST-DOSE, 4 HOURS POST-DOSE, 8 HOURS POST-DOSE)
	Subject taking OATP1B1 and/or OATP1B3 inhibitor (systemic route) at Screening	DV.DVREFID = IPD2A7
PK analysis set	Subject has no plasma concentration measurement after administration of study treatment	all PC.PCSTRESC = « » when PC.PCTPT not PRE-DOSE

ICF, informed consent form; OATP, organic anion transporting polypeptide; PK, pharmacokinetic(s).

Appendix C Definitions of marked abnormalities

The definitions of marked laboratory abnormalities are described in Idorsia standard document [REDACTED]

[REDACTED]

[REDACTED]

[REDACTED]

Appendix D Handling of missing or incomplete date and/or time

This section describes some general principles to be followed in the case of missing or incomplete date/time.

Note that unless noted otherwise, the non-imputed date/time will be reported in listings.

An incomplete (missing day or month) or missing AE/concomitant therapy date will be imputed as described in the table below. The 'lower limit' and 'upper limit' refer to the earliest and latest possible dates, respectively.

As an example: If start date is MAR2017 (missing day), the lower limit is 01MAR2017 and the upper limit is 31MAR2017; If start date is 2017 (missing day and month), the lower limit is 01JAN2017 and the upper limit is 31DEC2017.

Table 8 Handling of missing/incomplete date and time

Type of date	Date is incomplete	Date is missing
AE/CM resolution date	The upper limit.	No replacement, the AE/medication is considered as ongoing in the analysis.

Type of date	Date is incomplete	Date is missing
AE/CM onset date	
If the (imputed) resolution date is on or after the start of the study treatment and if the start of the study treatment falls within the upper and lower limits (inclusive), the study treatment start date is used.
 
If the resolution date is missing and the study treatment start date falls within the upper and lower limits (inclusive) the study treatment start date is used.
 
In all the other cases the lower limit is used.
	Whichever is the earlier of the date of resolution and the <study treatment> start date.

AE, adverse event; CM, concomitant medication.

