4.3 Inclusion criteria

For inclusion in the study, all of the following inclusion criteria must be fulfilled. It is not permitted to waive any of the criteria for any subject:

1. Signed informed consent prior to any study-mandated procedure.
2. Male and female subjects aged from 18–85 years, inclusive.
3. For women of childbearing potential: Negative urine pregnancy test at Visit 1 and at Visit 2 before randomization.
4. Stable CAD defined by the presence of any of the following conditions:
 - a. History of CAD with coronary artery stenosis on coronary angiogram $\geq 50\%$.
 - b. Previously documented MI occurring more than 3 months prior to randomization.
5. Antiplatelet background therapy stable for at least 1 month prior to randomization.
6. Body weight ≥ 40.0 kg (88.2 lbs).

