5.2.2 Reporting of previous/concomitant therapy in the case report form

The use of all study concomitant therapy (including contraceptives and traditional and alternative medicines, e.g., plant-, animal-, or mineral-based medicines) will be recorded in the CRF.

Previous therapies related to subject's underlying CAD will be recorded in the CRF if discontinued less than 1 month (≤ 30 days) prior to signing of the informed consent.

The generic name, start/end dates of administration (as well as whether it was ongoing at start of treatment and/or End-of-Study [EOS]), route, dose, and indication will be recorded in the CRF.

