10.7 Previous and concomitant medication

Previous medications are defined as any medication with a start date prior to study start date [see definition in Section 10.2.1] and with an end date (last administration) prior to or equal to study start date.

Study concomitant medications are defined as any medication that is ongoing after informed consent signature date, or initiated at any time between study start and up to EOS [see definition in Section 10.2.6].

Study treatment concomitant medications at baseline (a subset of study concomitant medications) are defined as any medication with a start date before date of study treatment administration and is either ongoing at end of study or has a stop date after the study treatment administration date.

Study treatment concomitant medications (a subset of study concomitant medications) are any medications that are either ongoing at study drug administration or initiated within a 2-day period from study treatment administration, i.e., on the day and the following day of study drug administration.

If no end date is available for a medication, it is considered ongoing, and is therefore both a *study concomitant medication* and a *study treatment concomitant medication*.

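### The shared AE/medication onset-date rule can move an ongoing antiplatelet drug with a missing or spanning start date to the injection day and out of the 'at baseline' background-therapy tables

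*SAP*

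**What the plan says.** Appendix D of the SAP treats the two kinds of record together: "An incomplete (missing day or month) or missing AE/concomitant therapy date will be imputed as described in the table below". In Table 8 the onset row is labelled for both AEs and concomitant medications and has three outcomes.

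- **Onset wholly missing:** "Whichever is the earlier of the date of resolution and the" study treatment start date.
- **Onset incomplete, range includes the study treatment start date:** the study treatment start date is used, provided the resolution date is missing or falls on or after that date.
- **Onset incomplete, all other cases:** the earliest possible date is used.

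For a missing resolution date the rule is "No replacement, the AE/medication is considered as ongoing in the analysis".

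SAP section 10.7 defines study treatment concomitant medications at baseline as "any medication with a start date before date of study treatment administration and is either ongoing at end of study", or with a stop date after dosing. SAP section 5.4.5 builds two things on that subset: the oral P2Y12 antagonists at baseline, and the seven categories running from neither aspirin nor a P2Y12 antagonist, through monotherapy, to dual therapy.

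Protocol section 4.3, criterion 5, requires "Antiplatelet background therapy stable for at least 1 month prior to randomization". Protocol section 5.2.2 has the CRF record start and end dates "as well as whether it was ongoing at start of treatment" or at end of study.

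**The concern.** Moving an uncertain onset towards the dosing date is cautious for an adverse event, because the event then counts as treatment-emergent. For a background drug it works the other way: a drug the subject was already taking is recorded as starting on Day 1. Section 10.7 asks for a start strictly before dosing, so the drug fails.

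That result conflicts with eligibility. Antiplatelet therapy that met criterion 5 cannot have begun on the injection day. The CRF item that would settle the matter is collected, but neither Table 8 nor section 10.7 uses it to decide baseline status.

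What is at stake is the description of the population. The primary objective refers to subjects on conventional oral antiplatelet background therapy. Protocol section 4.2 expects sufficient data on top of therapy that includes a P2Y12 antagonist. The tables in SAP section 5.4.5 are where a reader would check this.

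**Working it through.** The plan states no figure to reproduce, so the check applies Table 8 and then section 10.7 literally to test records. The injection date T = 15 March 2018 is illustrative.

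The rules as applied:
- Onset missing: start = the earlier of the stop date and T. If there is no stop date, start = T.
- Onset partial: start = T if the range includes T and the drug is ongoing or stopped on or after T. Otherwise start = earliest possible date.
- At baseline: start < T, and ongoing or stopped after T.

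| Recorded start | Stop | Imputed start | At baseline? |
|---|---|---|---|
| Missing | Ongoing | 15 Mar 2018 | No |
| Missing | 1 Apr 2018 | 15 Mar 2018 | No |
| Missing | 1 Mar 2018 | 1 Mar 2018 | No (correct) |
| 2018, year only | Ongoing | 15 Mar 2018 | No |
| Mar 2018, month only | Ongoing | 15 Mar 2018 | No |
| Jan 2018, month only | Ongoing | 1 Jan 2018 | Yes |
| 2015, year only | Ongoing | 1 Jan 2015 | Yes |
| 1 Jun 2015, complete | Ongoing | none needed | Yes |

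Four of the eight cases lose baseline status through the imputation: rows 1, 2, 4 and 5. Row 5 should be rare among eligible subjects, because a start in the dosing month is hard to square with a month of stable therapy. Rows 1, 2 and 4 are compatible with criterion 5.

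Nothing later in section 10.7 restores these drugs. Its closing sentence on missing end dates assigns them to the study concomitant and study treatment concomitant groups, not to the baseline subset.

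Consequences in section 5.4.5:
- Aspirin only, with an affected aspirin record: moves from category 2 to category 1 (neither drug class).
- Dual therapy, one record affected: leaves the dual categories, including category 7, for monotherapy with the other drug.
- Dual therapy, both records affected: moves to category 1.

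Each move is towards less background therapy.

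Size: the documents give no count of missing or partial start dates. With 108 subjects per arm (protocol section 10.5), k affected subjects shift a category share by k/108. For assumed values of k:
- k = 1: 1/108 = 0.9 percentage points
- k = 5: 5/108 = 4.6 percentage points
- k = 10: 10/108 = 9.3 percentage points

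**The case against.** The best case against is that little depends on these tables, and much of it stands.

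- The partial date one would expect for a long-standing drug is an earlier year or month, which Table 8 handles correctly.
- Affected records may be few. Start dates are required in the CRF, programmed queries apply, and monitors verify the inclusion criteria.
- A subject with a second record of the same drug that has a usable earlier date keeps it at baseline.
- An affected drug still counts as study treatment concomitant, is tabulated there by ATC code and INN, and is listed with its non-imputed date. This helps only in part. That table also includes drugs started after dosing, and it does not show who was on monotherapy or dual therapy.

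It could also be argued that section 10.7 means the recorded rather than the imputed date. Appendix D, however, reserves non-imputed dates for listings, and a blank date cannot satisfy a strict 'before' test either.

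A reader might infer more than the documents support:

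- **That the pharmacodynamic results inherit the error.** The tests on response rate do not use drug categories. The models in SAP sections 6.8.1.2 and 6.8.2.2 adjust for PRU stratum, and stratification uses measured Day 1 PRU. The planned subgroups are age, BMI, sex, diabetes and chronic kidney disease. Concomitant drug use is among the other objectives, but the SAP plans no analysis by antiplatelet category.
- **That affected P2Y12 users would leave the per-protocol set as apparent new starters.** SAP Table 7 uses deviation codes for those exclusions, not imputed dates.
- **That the 50% placebo response assumption is undermined.** Protocol section 10.5 gives it as a planning input and does not derive it from these categories.

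**Conclusion.** The fault is real and follows from the SAP's own text. An antiplatelet drug that is ongoing at dosing, or stopped after it, is excluded from the baseline subset if its start date is wholly missing or is a partial date spanning the injection day. The exclusion contradicts criterion 5 and always understates background therapy.

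Its reach is limited to the descriptive tables in SAP section 5.4.5 and any later look by concomitant drug. The primary tests, stratification, models and per-protocol set are unaffected. The number of affected records is unknown and could be zero. Multiplying an assumed share of incomplete records by 324 subjects would not give a valid estimate: the documents support no such share, and subjects on dual therapy contribute more than one record. The shift of 0.9 percentage points per affected subject assumes a full arm of 108 and no other qualifying record of the same drug.

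This is worth correcting because the stated rule gives a wrong classification and the data to avoid it are already collected.

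**What to change.** Either of two changes would do.

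1. Split the Table 8 onset row into an AE row and a medication row. In the medication row, when the CRF shows the drug ongoing at start of treatment and the start date is missing or spans the injection day, treat the drug as started before study treatment: use the earliest possible date for a partial date, and the day before dosing for a wholly missing one. Keep the current imputation for all other medication records.
2. Alternatively, define baseline status in SAP section 10.7 directly from that CRF item.

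The AE rule stays as it is. The cost is one SAP row or one definition, plus minor programming, with no new data. If no record is affected, the output does not change.
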